### **2.3.3 Anti-insulin antibody population**

The AIA population is defined as all patients from the safety population with at least one AIA sample available for analysis (ie, collected during the on-treatment period and at least 8 hours after the last administration of mealtime insulin). Patients will be analyzed according to the treatment actually received.

### **2.3.4 Efficacy population**

#### **2.3.4.1 *Intent-to-treat population***

The efficacy population will be the ITT population, which includes all randomized patients, irrespective of compliance with the study protocol and procedures.

Patients will be analyzed for efficacy analyses in the treatment group to which they are randomized.

## **2.4 STATISTICAL METHODS**

Continuous data will be summarized by treatment group (switching arm or non-switching arm) using, if not stated otherwise, the number of observations available (N), mean, SD, minimum, median, and maximum. These apply to all data, except PK data which will be described as detailed in [Section 2.5.7](#).

Categorical and ordinal data (except PK data, see [Section 2.5.7](#)) will be summarized by treatment group (switching arm or non-switching arm) using the number and percentage of patients.

In general, descriptive statistics of parameters (result and change from baseline, if applicable) by scheduled post-baseline visits will be provided on observed cases, ie, including only patients having non-missing assessments at a specific visit. All statistical analyses (descriptive statistics, plots, and statistical models) will be performed on visits defined using the reallocation algorithm of premature end of treatment provided in [Section 2.5.3](#).

#### **2.4.1 Demographics and baseline characteristics**

Parameters will be summarized on the randomized population analyzed in the treatment group to which they were randomized.

Analyses for the PK population will be performed if the size of the PK population is less than 90% the size of the randomized population for any treatment group.

Parameters described in [Section 2.1.1](#) will be summarized by treatment group and overall, using descriptive statistics.

Medical/surgical history will be summarized by primary SOC and PT in each treatment group and overall. Events will be sorted by SOC internationally agreed order and decreasing frequency of PT based on incidence in the overall treatment group.

No statistical test for the between-group difference will be performed.

#### **2.4.2 Prior or concomitant medications**

The prior, concomitant and post-treatment medications will be presented on the randomized population, separately for anti-diabetic medications and non-anti-diabetic medications. Anti-diabetic medications will be identified by a pre-defined list of ATC codes.

Medications will be summarized by treatment group and overall (only for prior medications) according to the WHO-DD dictionary. Non-anti-diabetic medications will be summarized considering the first digit of the ATC class (anatomic category) and the first 3 digits of the ATC class (therapeutic category). All ATC codes corresponding to a medication will be summarized, and patients will be counted once in each ATC category (anatomic or therapeutic) linked to the medication. Therefore, patients may be counted several times for the same medication. Anti-diabetic medications will be presented by pharmacological class (ATC3), chemical class (ATC4), and standardized medication name.

The tables for prior medications will be sorted by decreasing frequency within the ATC categories presented based on the overall incidence across treatment groups. In case of equal frequency, alphabetical order will be used.

The tables for concomitant and post-treatment medications will be sorted by decreasing frequency within the ATC categories presented based on the incidence in the switching arm. In case of equal frequency, alphabetical order will be used.

Frequency statistics including number of patients and percentage will be provided. No statistical test for the between-group difference will be performed.

#### **2.4.3 Extent of investigational medicinal product exposure and compliance**

The extent of IMP exposure will be assessed and summarized by actual treatment within the safety population ([Section 2.3.2](#)).

##### ***2.4.3.1 Extent of investigational medicinal product exposure***

The extent of IMP exposure will be assessed by the duration of the open-label IMP exposure and daily insulin doses (basal, mealtime, total).

### ***Observation period***

The observation period for exposure is defined as the time from the first injection of IMP up to the day of last injection of IMP.

### ***Duration of exposure***

The duration of exposure will be the total number of days of administration of the open-label IMP, ignoring temporary drug discontinuation (see [Section 2.5.1](#) for calculation in case of missing or incomplete data).

The duration of exposure to the open-label IMP will be defined in days as:

(Date of the last IMP administration – date of the first IMP administration) + 1

The process described in [Section 2.5.1](#) will be applied to define the date of the last IMP administration. If this date is missing, the IMP exposure duration should be left as missing.

Duration of IMP exposure will be summarized descriptively as a quantitative variable (number, mean, SD, median, minimum, and maximum). The number (n) and proportion (%) of patients exposed to the open-label IMP will be presented by specific time periods for each treatment group in the safety population.

The time periods of interest are grouped as follows:

- Up to 4 weeks,
- >4 to 8 weeks,
- >8 to 12 weeks,
- >12 to 15 weeks,
- >15 to 16 weeks,
- >16 to 24 week,
- >24 weeks.

The cumulative duration of exposure will be described using the following time periods:

- $\geq$  1 day,
- >4 weeks,
- >8 weeks,
- >12 weeks,
- >15 weeks,
- >16 weeks,
- >24 weeks.

Additionally, the cumulative duration of treatment exposure will be provided, defined as the sum of the duration of treatment exposure for all patients, and will be expressed in patient-years.

If the number of patients impacted by COVID-19 is sufficient, the duration of IMP exposure will also be presented by subgroup of COVID-19 impact (Non-impacted, Impacted) (see definition [Section 2.2](#)).

### ***Daily insulin doses***

All insulin doses will be reported by patient in e-diary, transferred to the IMP/NIMP e-diary page of the eCRF and reviewed by the investigator in dedicated items. In case the insulin doses reported by the patient are incorrect, the investigator will invalidate them and enter correct doses in the IMP/NIMP back-up e-diary page of the eCRF. For the analyses, the investigator entries will prevail when compared from the transferred e-diary data.

The process described in [Section 2.5.3](#) will be applied to assign visits to the insulin doses transferred from the e-diary webportal into the clinical database, and to retrieve doses in case of premature treatment discontinuation.

At baseline, the daily basal, mealtime, and total (basal plus mealtime) insulin doses (U and U/kg body weight) will be calculated as follows:

- Daily basal insulin dose at baseline (U and U/kg) = median of daily basal insulin doses available up to 7 days before the day of first IMP,
- Daily mealtime insulin dose at baseline (U and U/kg) = median of daily mealtime insulin doses available up to 7 days before the day of first IMP,
- Daily total insulin dose at baseline (U and U/kg) = median of daily total insulin doses available up to 7 days before the day of first IMP.

At Visit 3, daily insulin doses (basal, mealtime, and total) will be calculated as the median of daily insulin doses available in the week after the day of first IMP. At further visits, the daily insulin doses (basal, mealtime, and total) will be calculated as the median of daily insulin doses available in the week before the visit. Technical details related to the computation and handling of missing data are described in [Section 2.5](#).

The daily insulin doses (basal, mealtime, total) will be described at baseline, during the week after the date of the first IMP administration, then at each visit, and the changes from baseline will be presented. Figures will be provided.

The ratio of the daily basal insulin/total insulin dose observed and change from baseline will be described at baseline and at each visit.

The daily insulin doses (basal, mealtime, total) will be summarized according to categories of HbA1c change from baseline to Week 16 (<-1%, ≥-1% to ≤1%, >1%).

If the number of patients impacted by COVID-19 is sufficient, daily insulin doses will also be presented by subgroup of COVID-19 impact (Non-impacted, Impacted) (see definition [Section 2.2](#)).

Any technical details related to the calculation of doses and the imputations for missing data are described in [Section 2.5.1](#).

#### **2.4.3.2 Compliance**

Not applicable.

#### **2.4.4 Analyses of pharmacokinetic endpoints**

##### **2.4.4.1 Analyses of primary pharmacokinetic endpoints**

###### ***Primary analysis***

The primary analysis will be performed on the PK population, based on natural log-transformed  $AUC_{last}$ ,  $AUC$ , and  $C_{max}$ . The 90% CI for the ratio of geometric means for  $AUC_{last}$ ,  $AUC$ , and  $C_{max}$  between the two treatment arms (switching arm versus non-switching arm) should be within 80-125%, corresponding to the following composite null and alternative hypotheses tested at an alpha level of 0.05:

- $H_0$ : The ratio of geometric means for  $AUC_{last}$ ,  $AUC$ , or  $C_{max}$  between the switching arm and the non-switching arm is outside the predefined acceptance range 80-125%
- $H_1$ : The ratio of geometric means for  $AUC_{last}$ ,  $AUC$ , and  $C_{max}$  between the switching arm and the non-switching arm is within the predefined acceptance range 80-125%

For primary analysis, the natural log-transformed  $AUC_{last}$ ,  $AUC$ , and  $C_{max}$  will be statistically analyzed using an analysis of variance, including the fixed categorical effects of treatment arm (switching arm, non-switching arm) and randomization stratum (screening HbA1c <8.0%,  $\geq 8.0\%$ ).

Estimate and 90% CI for the ratio of geometric means between the two arms (switching arm / non-switching arm) will be computed separately for  $AUC_{last}$ ,  $AUC$ , and  $C_{max}$ , from the linear model framework using re-transformation. The 90% CIs for the ratio of geometric means of  $AUC_{last}$ ,  $AUC$ , and  $C_{max}$  should be within 80-125%.

Additionally, PK parameters will be summarized by treatment using descriptive statistics (for details, see [Section 2.5.7](#)).

### ***Subgroup analyses***

If it will be deemed necessary for interpretation of results, PK parameters may also be summarized for selected subgroups.

### ***Sensitivity analyses***

Exploratory statistical sensitivity analyses may be performed for primary PK parameters. They will be performed in a corresponding manner as the primary analysis, with

- Inclusion of those primary PK parameters affected by major deviations (ie., excluded from primary PK analysis)
- Exclusion of implausible PK parameters and PK parameters suspected to result from apparent but not documented PK irregularities.

#### ***2.4.4.2 Analysis of secondary pharmacokinetic endpoints***

$T_{max}$  will be summarized by treatment group in the PK population using descriptive statistics.

#### ***2.4.4.3 Multiplicity issues***

The type of analysis for multiple primary PK endpoints cannot inflate the type 1 error risk above 0.05. No adjustment of alpha/confidence level will be performed.

Further PK endpoints will be analyzed purely descriptively.

#### ***2.4.4.4 PK parameters at premature end of trial***

For patients with a PK profile at premature end of trial (PEOT), PK parameters will be derived.

Descriptive statistics of PK parameters from profiles at PEOT will be generated per treatment arm.

### ***2.4.5 Analyses of safety data***

The summary of safety results will be presented by treatment group.

#### ***General common rules***

All safety analyses will be performed on the safety population as defined in [Section 2.3.2](#), unless otherwise specified, using the following common rules:

- Safety data in patients who do not belong to the safety population (eg, exposed but not randomized) will be listed separately.
- The baseline value is defined as the last available value prior to the first injection of IMP. When the time of assessment is not available, the value is considered as baseline if assessment date is the date of 1st IMP intake.

- The potentially clinically significant abnormality (PCSA) values are defined as abnormal values considered medically important by the Sponsor according to predefined criteria/thresholds based on literature review and defined by the Sponsor for clinical laboratory tests, and vital signs, (PCSA criteria are provided in the ADaM metadata and in [Appendix A](#)).
- PCSA criteria will determine which patients had at least 1 PCSA during the on-treatment period, taking into account all evaluations performed during the on-treatment period, including nonscheduled or repeated evaluations. The number of all such patients will be the numerator for the on-treatment PCSA percentage.
- The treatment-emergent PCSA denominator by group for a given parameter will be based on the number of patients assessed for that given parameter in the on-treatment period by treatment group on the safety population.
- For quantitative safety parameters based on central laboratory measurements, descriptive statistics will be used to summarize results and change from baseline values by visit and treatment group. Summaries will include the last on-treatment value. The last on treatment value is defined as the value collected at the same day/time of the last dose of IMP. If this value is missing, this on-treatment value is the closest one prior to the last dose intake.
- The analysis of the safety variables will be descriptive, and no systematic testing is planned.

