## 1.4 STUDY PLAN

The following figure describes the design of the study:

FPG: fasting plasma glucose; HbA1c: glycated hemoglobin A1c; PK: pharmacokinetics; T1DM: Type 1 diabetes mellitus; \* prior to the screening visit

The study comprises up to 4 periods:

- An up to 14-day screening period
- An up to 12-week run-in period (only for patients not treated with NovoLog and insulin glargine (100 U/mL) for at least 12 weeks before screening)
- A 16-week open-label treatment period:
  - Participants in the non-switching arm will receive NovoLog for 16 weeks,
  - Participants in the switching arm will receive NovoLog for the first 4 weeks, then SAR341402 for 4 weeks, followed by NovoLog for 4 weeks and then SAR341402 for the last 4 weeks.
- A 1-day post-treatment follow-up period.

The study duration per participant will be less than 19 weeks (for participants who do not require the run-in period) and less than 31 weeks (for participants who require the run-in period).

At the end of the 16-week open-label treatment period, patients will have blood sampling, including for PK determination, antibody measurements, HbA1c, and FPG. After blood sampling for the trough PK measurements, patients will receive a single SC injection of 0.15 U/kg SAR341402 (switching arm) or NovoLog (non-switching arm). Subsequently, PK sampling will be conducted for 8 hours according to assessment schedule; see pharmacokinetic flow chart in Section 1.3 of the protocol.

The end of treatment (EOT) is at Visit 7 (Week 16) after randomization. The end of the study (EOS) is a follow-up contact (Visit 8, recorded as Visit 8010 in the clinical database) at the time of Week 16 plus 1 day.

In case of premature permanent investigational medicinal product (IMP) discontinuation, the patients will have a premature treatment discontinuation visit (recorded as Visit 8000 in the clinical database), which will consist of all procedures planned for Visit 7 and is intended to be conducted before the definitive discontinuation of the IMP, or as soon as possible after discontinuation.

Patients who discontinue study intervention should remain in the study, with the remaining visits occurring as scheduled where possible, including the assessments planned in the SoA (see Section 1.3 of the protocol) except serial PK samples that should only be collected at the time of early discontinuation visit and do not need to be repeated at Visit 7 (Week 16).

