### ***Safety observation period***

The observation period for safety data will be divided into 3 main segments:

- The **pre-treatment period** is defined as the time from informed consent up to the time of the first injection of IMP.
- The **on-treatment period** is defined as the time from the first injection of IMP up to the last injection of IMP + 1 day (included).
- The **post-treatment period** is defined as the time from the last injection of IMP + 2 days (included).

Analyses will focus on safety observations during the on-treatment period.

The **on-study observation period** is defined as the time from first injection of IMP until the end of the study (defined as the date of end of participation).

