#### ***2.4.5.4 Analyses of laboratory variables***

The summary statistics (including number, mean, median, standard deviation, minimum, and maximum) of all laboratory variables (central laboratory values and changes from baseline) will be calculated for each visit or study assessment (baseline, Week 16, and last on-treatment value)

by treatment group. This section will be organized by biological function as specified in [Section 2.1.5.4](#).

The incidence of PCSAs (list provided in [Appendix A](#)) at any time during the on-treatment period will be summarized by biological function and treatment group whatever the baseline level and according to the following baseline status categories:

- Normal/missing,
- Abnormal according to PCSA criterion or criteria.

For parameters for which no PCSA criteria are defined, similar table(s) using the normal range will be provided.

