### ***End of treatment visit***

If a patient discontinues the treatment prematurely, end of treatment (Visit 8000) assessments will be re-allocated to the next scheduled on-site visit for the patient, except for the PK assessments, as the PK profiles of patients who prematurely discontinued the treatment will not be included in the primary PK analysis.

The next scheduled on-site visit for each patient will be determined as the next on-site visit that should be performed as per protocol, following the last visit actually performed by the patient before Visit 8000.

For a given parameter, the value will not be re-allocated in the following cases:

- If the parameter is not planned to be collected at the re-allocation visit.
- If a value is already available for the parameter at the re-allocation visit.

This process will be used to retrieve all assessments (except PK assessment) performed at the end of treatment visit (Visit 8000) and will apply to insulin doses assigned to Visit 8000 following the process described above.

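### When an early stopper's Visit 8000 labs follow the last dose, the SAP's last on-treatment rule passes over them and can return the baseline value instead

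*SAP*

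**What the plan says.** **Last on-treatment value.** SAP 2.4.5 (General common rules), in a bullet on quantitative parameters measured by the central laboratory: "The last on treatment value is defined as the value collected at the same day/time of the last dose of IMP". The fallback is: "If this value is missing, this on-treatment value is the closest one prior to the last dose intake". The same list sets baseline: "The baseline value is defined as the last available value prior to the first injection of IMP". SAP 2.5.4 adds that both scheduled and unscheduled central-laboratory values are eligible.

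**Where it is used.** SAP 2.4.5.4 summarizes each laboratory variable at "baseline, Week 16, and last on-treatment value". SAP 2.4.5.5 uses the same term for vital signs and weight.

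**On-treatment period.** SAP 2.1.5: it "is defined as the time from the first injection of IMP up to the last injection of IMP + 1 day (included"). Protocol 9.4.3 sets the same limit. The general PCSA count, numerator and denominator, uses this window. The drug-induced liver injury paragraph in SAP 2.4.5.4 instead counts PCSAs at all visits after baseline.

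**Visit 8000.** SAP 1.4 gives it all Visit 7 procedures and says it "is intended to be conducted before the definitive discontinuation of the IMP, or as soon as possible after discontinuation". SAP 2.5.3 moves its results to the next scheduled on-site visit, with two exceptions. One is that the target visit already has a value. The other is: "If the parameter is not planned to be collected at the re-allocation visit".

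**Lab schedule.** In Protocol 1.3.1 and 1.3.2, hematology and chemistry fall at Visit 1, at Visit 3 (run-in participants only) and at Visit 7. None is planned at Visits 4, 5 or 6.

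**The concern.** A last on-treatment column exists so that people who leave early still contribute their end-of-treatment result. Here the rule looks only at the day of the last dose and backwards, and it states no lower limit at the first dose. With no labs scheduled during treatment, looking backwards can lead straight to baseline. A participant who was exposed, stopped and then had blood drawn could be tabulated as unchanged on the strength of a sample taken before any IMP.

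The rule also disagrees with the SAP's own window. A sample on day +1 is on-treatment for PCSAs but cannot be the last on-treatment value. The re-allocation process, which SAP 2.1.5 says is there to retrieve Visit 8000 safety data, does not help most early stoppers' labs, because Visits 4 to 6 have no laboratory slot. At stake is the laboratory safety summary for the very participants whose post-exposure results are of most interest.

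**Working it through.** The plan gives no figure for this point, so the check applies the rules to cases.

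**Step 1. Why the fallback lands on baseline.** Fallback = latest value at or before the last dose. Baseline = latest value before the first injection. If no lab exists between first injection and last dose, the two definitions select the same sample, so change = baseline - baseline = 0. If the words this on-treatment value are read as requiring a sample after the first injection, no value qualifies and the result is missing. The Visit 8000 sample is used under neither reading.

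**Step 2. Cases.** Planned days: Visit 4 = 28, Visit 5 = 56, Visit 6 = 84, Visit 7 = 112.

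| Last dose | Visit 8000 | Other labs | By-visit table | Last on-treatment value | General PCSA count of Visit 8000 lab |
|---|---|---|---|---|---|
| Day 40 | Day 40 | none | no slot (next is Visit 5) | Visit 8000 | counted |
| Day 42 | Day 40 | none | no slot | Visit 8000 | counted |
| Day 40 | Day 41 | none | no slot | baseline (change 0) or missing | counted |
| Day 40 | Day 45 | none | no slot | baseline (change 0) or missing | excluded |
| Day 40 | Day 45 | unscheduled central lab, Day 20 | no slot | Day 20 lab | excluded |
| Day 100 | Day 105 | no Visit 7 value | Week 16 | baseline (change 0) or missing | excluded |
| Day 100 | Day 105 | Visit 7 value present | not re-allocated | baseline (change 0) or missing | excluded |

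Rows 1 and 2 show the rule working. Row 3 is the internal mismatch: one sample is on-treatment for PCSAs and ineligible for the last on-treatment value. Row 6 puts the Visit 8000 result in the Week 16 column while the neighbouring last on-treatment column shows baseline or nothing.

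**Step 3. How a late Visit 8000 can arise.** SAP 1.4 allows it. In addition, Protocol 7.1.2 treats stops as temporary at first and as definitive once interruptions total more than 10 days. For one continuous interruption converted this way, a visit prompted by that decision comes more than 10 days after the last dose, beyond the +1 day limit.

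**Step 4. Size.** The documents give no early-stopping rate. Per arm, 184 / 2 = 92.
- Assumed 5%: 0.05 x 92 = 4.6. Assumed 10%: 0.10 x 92 = 9.2.
- The sample-size allowance is 184 - 146 = 38 (38 / 184 = 20.7%), or 19 per arm. It covers every reason for being non-evaluable for PK, so it is a loose outer figure.

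These are ceilings, because every stopper would have to meet all the conditions. On the literal reading, if a fraction f of an arm is set to 0 and their true mean change is M, the arm's mean change is off by f x M: 0.05M to 0.10M at the assumed rates.

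Stops before Visit 6 cover 84 / 112 = 75% of the treatment period. That is the share of stops without a by-visit slot only if stops are spread evenly over time, which is an assumption.

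**The case against.** A reader might infer that the SAP discards the Visit 8000 labs of all early stoppers and records each as zero change. The documents do not support that, for these reasons:

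- **The planned path works.** Visit 8000 is meant to precede the stop. The PK flow chart (Protocol Table 1) covers the early discontinuation visit, and at Week 16 the profile follows an IMP injection, so an injection that day is a fair inference. The labs then fall on or before the day of the last dose and are used.
- **Zero is only one reading.** The fallback speaks of an on-treatment value, and on-treatment begins at the first injection. Missing is at least as natural.
- **Re-allocation does not govern the last on-treatment value.** SAP 2.5.4 draws it from all scheduled and unscheduled central labs. Protocol 7.1.1 has clinically significant abnormal values rechecked before a definitive stop, so a participant stopping for a laboratory finding may well have an eligible unscheduled sample, if it was run centrally and taken by the last dose.
- **The results are not lost overall.** PCSA counts keep labs to day +1. Early stoppers remain in follow-up with Visit 7 labs still planned. Clinically relevant changes are recorded as AEs, and ALT above 3 x ULN is an AESI.
- **Vital signs.** The definition is written for central-laboratory parameters only. For vital signs and weight, the SAP uses the term without defining it.

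All of this stands, and it narrows the point. It does not remove it. Two programmers could derive different tables from the same text, and under either reading a late Visit 8000 result is passed over. A Visit 7 lab does not replace it: after a Day 40 stop it comes 112 - 40 = 72 days later. Leaving labs from day +2 out of the general PCSA count follows the protocol's window and is a choice rather than an error, but the liver paragraph does not apply the same window.

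**Conclusion.** The point holds under stated conditions: Visit 8000 labs drawn after the last dose, and no unscheduled central lab on treatment. The last on-treatment value is then baseline with a change of exactly 0, or missing, depending on the reading. The day +1 conflict with SAP 2.1.5 exists on either reading. The missing by-visit slot when the next visit is 4, 5 or 6, and the different window in the liver paragraph, add to the inconsistency.

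The effect is confined to descriptive laboratory safety summaries for a small number of early stoppers that the documents do not state. The 5-9 per arm is a ceiling resting on an assumed stopping rate. The primary PK analysis is untouched. On the literal reading the direction is toward showing no change, which is the wrong direction for a safety table. The change is worth making because it is specific and nearly free.

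**What to change.** 1. In SAP 2.4.5, define the last on-treatment value as the last post-baseline central-laboratory value from the first IMP injection through the last injection + 1 day. If there is none, set it to missing. State that a value taken before the first injection is never used.
2. Summarize or list Visit 8000 labs drawn after that window separately, with days since last dose. This also covers labs that SAP 2.5.3 leaves without a by-visit slot.
3. Align the window of the liver PCSA paragraph in SAP 2.4.5.4 with the general rule.
4. Apply the same definition to vital signs and weight in SAP 2.4.5.5.

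Counting Visit 8000 labs as on-treatment however late they are drawn is not advised: it would contradict the +1 day limit in Protocol 9.4.3, and Protocol 6.5 allows any antidiabetic medication after a definitive stop.

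Cost: minor SAP and ADaM rework, and a few more missing values in the last on-treatment table. No change to data collection.
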